5.1. Inclusion Criteria

In order to be eligible to participate in this study, an individual must meet **all** of the following criteria:

- 5.1.1 Histologically or cytologically confirmed metastatic Stage IV adenocarcinoma of the pancreas
- 5.1.2 No prior treatments for stage IV pancreatic adenocarcinoma (prior adjuvant or neoadjuvant treatment is allowed provided completed \geq 6 months prior to disease recurrence)
- 5.1.3 Eastern Cooperative Oncology Group (ECOG) performance status 0 – 1¹⁷
- 5.1.4 Male and female patients 18 – 75 years of age
- 5.1.5 Measurable disease determined using guidelines of Response Evaluation Criteria In Solid Tumors (RECIST version 1.1)
- 5.1.6 Expected survival >3 months
- 5.1.7 Women of child-bearing potential (i.e., women who are pre-menopausal or not surgically sterile) must use accepted highly effective contraceptive methods (abstinence, intrauterine device [IUD], oral contraceptive(s), intrauterine hormone releasing system (IUS), bilateral tubal occlusion or vasectomized partner) during and for 6 months after last study dose and must have a negative serum or urine pregnancy test within 1 week prior to treatment initiation, at monthly interval (*day 1 of every even numbered cycle*), at the end of systemic exposure, and at 30 days after the systemic exposure
- 5.1.8 Males with female partners (of childbearing potential) and female partners (of child bearing potential) with male partners must agree to use double barrier contraceptive measure (a combination of male condom with either cap, diaphragm or sponge with spermicide) in addition to oral contraception or avoidance of intercourse during the study and for 6 months after last study dose is received
- 5.1.9 At least 2 weeks must have elapsed from any prior surgery with resolution of any sequela for randomization
- 5.1.10 Laboratory values \leq 2 weeks prior to randomization must be:
 - Adequate hematologic values
 - Platelet count \geq 100,000 cells/mm³ or \geq 100 bil/L:
 - Absolute neutrophil count [ANC] \geq 1,500 cells/mm³ or \geq 1.5 bil/L:

- Hemoglobin ≥ 9 g/dL or ≥ 90 g/L)
- Adequate hepatic function
 - Aspartate aminotransferase [AST/SGOT] ≤ 3 x upper normal limit [UNL] (≤ 5 x UNL if liver metastases present)
 - Alanine aminotransferase [ALT/SGPT] ≤ 3 x UNL (≤ 5 x UNL if liver metastases present)
 - Bilirubin (≤ 1.5 x UNL); bilirubin ≤ 2.5 x ULN for subjects with Gilbert's syndrome
 - Serum albumin ≥ 3.0 g/dL
- Adequate renal function

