5.3.1. Discontinuation of Treatment

The Investigator must protect the subject's welfare and may discontinue any study treatment at any time when this action appears to be in the subject's best interest. The reason for the subject's discontinuation must be recorded in the subject's electronic case report. Possible reasons for the discontinuation may include, but are not limited to, the following:

- Disease Progression defined as follow: disease progression documented by CT scan (or MRI) based on RECIST version 1.1 criteria, as determined in the protocol;
- Adverse Event;
- Any significant Protocol Violation as per protocol;
- Withdrawal of consent by an enrolled subject.

5.3.1.1 Patients requiring delay for more than 3 weeks because of toxicity.

- 5.3.1.2 Unacceptable toxicity from FFX or mFFX + devimistat (Grade 3 or more severity of toxicity).
- 5.3.1.3 The subject becomes pregnant (treatment should be discontinued immediately)
Intercurrent illness with a condition, injury, or disease unrelated to the intended disease for which the study is investigating, that renders continuing the treatment unsafe or regular follow-up impossible.
- 5.3.1.4 General or specific changes in the patient's condition that in the opinion of the treating physician renders the patient ineligible for further investigational treatment.
- 5.3.1.5 Recurrent grade 4 adverse events despite all appropriate dose reductions.
- 5.3.1.6 Non-compliance with investigational treatment, protocol-required evaluations or follow-up visits.
- 5.3.1.7 Other reasons as determined by the Investigator or Sponsor: A subject may have study treatment discontinued if, in the opinion of the Investigator or Sponsor, it is not in the subject's best interest to continue; Unambiguous clinical progression documented by the Investigator in the absence of radiological confirmation.

Subjects who discontinue all study medication for any reason should remain in the study for long-term follow up assessments unless they withdraw informed consent, die, or become lost to follow up. Long-term follow up evaluations will be performed accordingly as described in the protocol. In the event of study treatment discontinuation, the subject should be instructed to report to the site as early as possible after the decision to discontinue study treatment has been made. All End of Treatment procedures should be performed according to the protocol.

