5.3.2.1 Patient withdrawal of consent

5.3.2.2 Participation in any other trial during the subject's participation in this trial

In case of withdrawal, patient(s) will be asked to continue safety and survival follow-up every 2 months.

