7.3.4. End of Treatment Visit

Subjects should return to the study site for an End of Treatment Visit within approximately 7 days after treatment discontinuation of all study medication (CPI 613[®] + mFFX or FFX) and prior to initiation of subsequent anticancer therapy. Adverse events and concomitant medications will be reviewed at this visit, and the following assessments should be completed:

- Physical Examinations
- Vital Signs
- ECOG Performance Status
- Obtain CT scan (or MRI) if radiologic disease progression was not documented in the previous CT scan (or MRI) unless the latter one was performed within the last 14 days
- Blood sample collection for the following tests: Hematology, Blood Chemistry, and CA 19-9

- Collect AE and SAE
- Pregnancy test
- NCCN-FACT FHSI-18 Questionnaire

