7.3.5. Long-Term Follow-up

After the End of Treatment visit, subjects will enter long-term follow-up during which information on the subject’s survival status, disease progression and subsequent anticancer therapy will be obtained by the site every 2 months according to the protocol with a time window of +/- 7 days. Information may be collected by chart review, phone calls, clinic visits, or other means as appropriate. Long-term follow-up will continue until the subject dies, is lost to follow up, or withdraws consent.

Follow up for OS:

OS will be monitored every 2 months via telephone contact, review of hospital records, death records, social media, etc. as allowed by local laws after treatment termination (Note: During every post-study treatment telephone contact, information related to cancer treatment received will also be collected). OS and PFS will be calculated from the day of randomization.

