7.3.6. Schedule of Events Table

Table 16 Schedule of Events: Experimental Arm

Experimental Arm: devimistat + mFFX								
Assessments	Pre-Study Screen	Cycle 1 (+/- 24 hr.) and Subsequent Cycles (+/- 24 hr.)					End of treatment	Follow-Up Every 2 Months Until Death
		Day 1	Day 2	Day 3	Day 4	Days 5-14		
Informed consent	√							
Medical history	√							
Pregnancy test for women of childbearing Potential (monthly- day 1 of even numbered cycle)	√	√					√	
Hemoglobin A1c (HbA1c)	√							
devimistat administration (dosing)		√		√				

A Phase III Multi-Center Open-Label Randomized Trial to Evaluate Efficacy and Safety of FOLFIRINOX (FFX) versus Combination of CPI-613 with modified FOLFIRINOX (mFFX) in Patients with Metastatic Adenocarcinoma of the Pancreas

Protocol: PANC003

Version 9.0

June 10, 2021

mFOLFIRINOX (mFFX)		√	√	√				
AE and Con. Med. Assessment		AEs and con meds will be assessed at each patient visit						
Myeloid growth factor (as per institutional guidelines)*					√			
Evaluation of symptoms and vital signs ⁷	√	√					√	
ECOG performance status ⁶ and survival	√	√					√	
Clinical chemistry, hematology and coagulation	√	√				√ (day 7 or 8)	√	
Triphase contrast CT of the chest, abdomen and pelvis (or MRI if needed) (every 8 weeks)	√						√ (unless one was performed within the last 14 days)	
Blood sampling for biomarker ¹	√							
CA19-9 (every 8 weeks up to 12 cycles and every 4 weeks beyond 12 cycles)	√	√					√	
Blood sampling for Full PK Analysis ²		√		√				
Blood sampling for Sparse PK Analysis ³		√		√				
Cardiac Marker (Troponin I) ⁸		√		√				
Full ECG ⁴		√		√				
Sparse ECG ⁵		√		√				
Phone contact								√
NCCN-FACT FHSI-18 Questionnaire ⁶	√	√					√	

*Myeloid growth factor can be given at Day 4 or any day at the discretion of the treating physician per ASCO and institutional guidelines

¹ Prior to treatment initiation (within 4 weeks prior to 1st dose) and prior to each restaging scan.

² Full PK analysis will be carried out only for cycle 1. For Full PK sampling schedule see Section 7.1.1, Table 12

³ see Sparse PK sampling schedule in Section 7.1.1, Table 13

⁴ Full ECG measurement will be carried out only for cycle 1. For Full ECG measurement schedule see Section 7.1.1, Table 14

⁵ see Sparse ECG measurement schedule in Section 7.1.1, Table 15

⁶ at baseline and day 1 of every even numbered cycle

⁷ Vital signs include heart rate

⁸ see Cardiac Marker (Troponin I) schedule under Section 7

Table 17 Schedule of Events: Control Arm

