8.3. Time Period and Frequency for Event Assessment and Follow-Up

The occurrence of an AE or SAE may come to the attention of study personnel during study visits and interviews of a study participant presenting for medical care, or upon review by a study monitor. All AEs including local and systemic reactions not meeting the criteria for SAEs will be captured in the CRF. Information to be collected includes event description, time of onset, clinician's assessment of severity, relationship to study product (assessed only by those with the training and authority to make a diagnosis), and time of resolution/stabilization of the event. All AEs occurring while on study must be documented appropriately regardless of relationship, action taken with study drug (drug withdrawn, dose reduced), other treatment for AE (drug therapy, other procedure) and outcome of AE. All AEs will be followed to adequate resolution (return to baseline).

Any medical condition that is present at the time that the participant is screened will be considered as baseline and not reported as an AE. However, if the study participant's condition deteriorates at any time during the study, it will be recorded as an AE. UPs will be recorded in the data collection system throughout the study.

Changes in the severity of an AE will be documented to allow an assessment of the duration of the event at each level of severity to be performed. AEs characterized as intermittent require documentation of onset and duration of each episode. Disease progression will not be considered as an AE/SAE.

The PI will record all reportable events with start dates occurring any time after informed

consent is obtained until 7 (for non-serious AEs) or 30 days (for SAEs) after the last dose of the study drug. At each study visit, the investigator will inquire about the occurrence of AE/SAEs since the last visit. Events will be followed for outcome information until resolution or stabilization.

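### The protocol requires SAE recording and a pregnancy test out to 30 days after the last dose, but schedules no contact between End of Treatment and the first 2-monthly follow-up

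*Protocol*

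**What the plan says.** Two protocol provisions point to day 30. Section 8.3 sets the recording period for events as "until 7 (for non-serious AEs) or 30 days (for SAEs) after the last dose of the study drug". Criterion 5.1.7 requires pregnancy tests in women of childbearing potential "at the end of systemic exposure, and at 30 days after the systemic exposure".

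Section 8.3 ties active ascertainment to visits: "At each study visit, the investigator will inquire about the occurrence of AE/SAEs since the last visit". The AE row of Tables 16 and 17 does the same.

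The post-treatment schedule is as follows.

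- Sections 5.3 and 7.3.4 place the End of Treatment visit "within approximately 7 days after treatment discontinuation of all study medication". It includes AE and SAE collection and one pregnancy test.
- Section 7.3.5 then starts long-term follow-up: survival status, "disease progression and subsequent anticancer therapy will be obtained by the site every 2 months according to the protocol", with a window of 7 days either side. Chart review, phone calls and clinic visits are all allowed.
- In Tables 16 and 17 the column after End of Treatment is "Follow-Up Every 2 Months Until Death". Only phone contact is ticked in it.
- Section 5.3.2 mentions safety follow-up, but only for patients who withdraw, who "will be asked to continue safety and survival follow-up every 2 months".

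SAP Appendix I differs. In both arms it has a column for a contact 30 days after the last dose, with the pregnancy test marked, and it has no End of Treatment column.

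**The concern.** The 7-day window for non-serious events roughly matches the End of Treatment visit. The 30-day SAE window and the day-30 pregnancy test match nothing in the schedule that sites will follow. A site that carries out every scheduled step exactly as written can reach the first 2-monthly contact without having asked about SAEs after End of Treatment, and it need not ask then either.

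Four things are at stake.

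- **SAE counts.** The occurrence of at least one SAE is a named safety outcome (Protocol Section 9.4.4), and SAP Section 6.3.3 tabulates SAEs by arm.
- **Reporting speed.** The 24-hour clock in Section 8.4.2 starts at site awareness, so late discovery delays expedited reporting and review by the data monitoring committee.
- **Pregnancy.** Protocol Section 2.1.4.4.6 states that no reproductive or developmental toxicology studies have been done. The day-30 test is the protocol's own safeguard, and a phone call cannot supply a sample.
- **Comparability.** Both arms share the schedule, but the gap depends on how treatment ends. If the reasons for stopping differ by arm, SAE capture could differ too. This is an inference, and its direction is unknown.

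**Working it through.** The plan gives no figure of its own on this point, so the check is day arithmetic on the schedule.

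**Inputs**

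- SAE window: 30 days after the last dose (Section 8.3).
- End of Treatment: up to about 7 days after discontinuation (Section 7.3.4).
- Follow-up: every 2 months, plus or minus 7 days (Section 7.3.5).
- Month length: 30.4375 days (SAP Section 5.6), so 2 months = 2 × 30.4375 = 60.9 days, and the window runs from 53.9 to 67.9 days.
- Cycle: 14 days, with dosing ending on Day 3 (Tables 7 and 8).
- Late stopping rule in Section 5.3.1: "Patients requiring delay for more than 3 weeks because of toxicity".

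**Formulas**

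Let E be the day of the End of Treatment visit, counted from the last dose.

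- Days of the SAE window with no scheduled inquiry = 30 − E (zero if E is 30 or more).
- Next scheduled contact = E + 53.9 to E + 67.9, if the 2-month clock starts at End of Treatment.

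**Value of E by stopping pattern**

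- Discontinuation dated to the last dose: E = 0 to 7.
- Stop decided at the next Day 1, which is Day 15 of the previous cycle: 15 − 3 = 12 days after the last dose. With the visit 0 to 7 days later, E = 12 to 19.
- Toxicity delay of more than 21 days from that Day 1: E is above 12 + 21 = 33.

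| Stopping pattern | E | Days without inquiry (30 − E) | Next contact | Days after window closes |
|---|---|---|---|---|
| Stop at last dose, visit the same day | 0 | 30 | 54 to 68 | 24 to 38 |
| Stop at last dose, visit on day 7 | 7 | 23 | 61 to 75 | 31 to 45 |
| Stop decided at next Day 1 | 12 to 19 | 18 to 11 | 66 to 87 | 36 to 57 |
| Stop after toxicity delay of more than 3 weeks | above 33 | 0 | – | – |

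If the 2-month clock starts at the last dose instead, the first follow-up falls on about day 54 to 68 whatever the value of E. The earliest possible follow-up under either reading is therefore about day 54, so no scheduled follow-up contact can serve day 30.

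**Content of the contacts**

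| Requirement | End of Treatment | Day 30 | 2-monthly follow-up |
|---|---|---|---|
| SAE inquiry (8.3) | Yes | Not scheduled | Not listed in 7.3.5 or Tables 16–17 |
| Pregnancy test (5.1.7) | Yes | Required by 5.1.7, not scheduled | Not listed |

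The End of Treatment test can serve as the first of the two post-exposure tests. The second has no place in the schedule.

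**The case against.** The strongest reply is that the obligations exist whether or not a table has a column for them. Criterion 5.1.7 itself sets the day-30 test. Section 8.3 defines reportable SAEs by start date, so an event with onset on day 20 is still recordable if the site hears of it at the 2-month call. The same section requires events to be followed until they resolve or stabilize, which keeps some patients in contact after End of Treatment. Sites may use chart review, deaths are followed in any case, and SAP Section 6.3.3 summarizes cause of death. The day counts also depend on assumptions about when discontinuation is dated and when the 2-month clock starts.

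Part of this stands. Fatal events are unlikely to be lost, a late-discovered SAE can still be entered, and the size of the gap depends on the stopping pattern. The documents do not say how often each pattern occurs, so neither a typical gap nor a number of affected SAEs can be given.

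The rest does not remove the point. Following a known, unresolved event is not a query for new ones. Chart review under Section 7.3.5 is listed for survival, progression and later therapy, not SAEs. The inquiry rule in Section 8.3 refers to study visits, and whether a phone call counts as one is at best arguable. The day-30 column in SAP Appendix I does not help sites, which work from the protocol.

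**Conclusion.** The concern holds. The current protocol sets two day-30 requirements and schedules no contact that meets either, except incidentally when treatment ends after a toxicity delay of more than 3 weeks. Otherwise 11 to 30 days of the 30-day SAE window have no scheduled inquiry: 23 to 30 days if discontinuation is dated to the last dose, and 11 to 18 if the stop is decided at the next Day 1. These figures assume nominal 14-day cycles and an End of Treatment visit within 7 days of discontinuation.

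The consequence is late or incomplete capture of non-fatal SAEs and an unscheduled pregnancy test. Overall survival, type I error and power are not affected. It should be corrected, but it does not threaten the primary result.

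**What to change.** - Add a contact 30 days after the last dose to Tables 16 and 17 and to Section 7.3.5. It should carry an SAE query for all patients, by phone if needed, and a serum or urine pregnancy test for women of childbearing potential.
- At the first 2-monthly follow-up, add an SAE look-back to day 30 for any patient whose 30-day contact was missed.
- Align SAP Appendix I with the protocol tables, so that both show the End of Treatment visit and the 30-day contact.
- Leave the 30-day requirements in 5.1.7 and 8.3 as they are.

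The cost is one short contact per patient. The pregnancy test needs a sample, but 5.1.7 already requires it.

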8.4. Reporting Procedures

8.4.1. Adverse Event Reporting

At each visit the subject will be queried on changes in his/her condition. During the reporting period of the trial any untoward changes in the subject's condition will be recorded as AE, whether reported by the subject or observed by investigator.

Any treatment-emergent abnormal laboratory result which is clinically significant (defined as meeting one or more of the below must be documented on the CRF.

1. Accompanied by clinical symptoms
2. Leading to a change in study medication (e.g., dose modification, interruption or permanent discontinuation)
3. Requiring a change in concomitant therapy (e.g., addition of, interruption of, discontinuation of, or any other change in a concomitant medication, therapy or treatment)

It is the responsibility of the investigator to document all AEs that occur during the study. AEs should be reported on the appropriate page of the CRF. AEs should be reported for their actual grade and duration. The severity of the AE will be graded according to the NCI CTCAE Grading Scale (Current version).

8.4.2. Serious Adverse Event Reporting

Timeframes:

The study clinician will complete a SAE Form within the following timelines:

- All deaths and immediately life-threatening events, whether related or unrelated, will be recorded on the SAE Form and submitted to the Covance safety/study sponsor within 24 hours of site awareness.
- Other SAEs regardless of relationship, will be submitted to the Covance safety/study sponsor within 24 hours of site awareness.

Description:

All SAEs will be followed until satisfactory resolution or until the site investigator deems the event to be chronic or the adherence to be stable. Other supporting documentation of the event may be requested by the DCC/study sponsor and should be provided as soon as possible.

Study staff are responsible for completing and signing off on the SAE reports & Receiver of Notification of SAEs:

All SAEs which are serious, possibly related and unexpected are required to be reported to Covance using a serious adverse event report form. The SAE should be accompanied by relevant subject's medical records, the eCRF and other important documents.

SAE reports must be submitted to Covance PV by phone, fax or email to the following address:
Covance, Inc.

Covance PV and DSS

Email: [contact]

USA [contact]

EU: [contact]

When events are reported to various oversight and regulatory groups:

The investigator will also assure that all AEs meeting IRB/IEC and regulatory authorities' criteria are documented and communicated appropriately. All documentation and communications to the IRB/IEC and applicable regulatory authorities will be provided to the Sponsor and maintained within the Trial Master File.

8.4.3. Unanticipated Problem Reporting

Incidents or events that meet the OHRP criteria for UPs require the creation and completion of an UP report form. It is the site investigator's responsibility to report UPs to their IRB and to the DCC/study sponsor. The UP report will include the following information:

1. Protocol identifying information: protocol title and number, PI's name, and the IRB project number;
2. A detailed description of the event, incident, experience, or outcome;
3. An explanation of the basis for determining that the event, incident, experience, or outcome represents an UP;
4. A description of any changes to the protocol or other corrective actions that have been

taken or are proposed in response to the UP

To satisfy the requirement for prompt reporting, UPs will be reported using the following timeline:

1. UPs and SUSARs will be reported to regulatory authority/sites/central IRBs by day 7 for initial reports for fatal and life-threatening events and day 15 for all other events
2. Sites should send UPs to their local IRBs and institutions as appropriate per SOPs

8.5. Safety Oversight

Safety oversight will be under the direction of a DMC composed of individuals with the appropriate expertise, including medical oncology with experience treating metastatic pancreatic cancer patients, statistical analysis. The DMC will meet at least semiannually to assess safety and efficacy data on each arm of the study. The DMC will operate under the rules of an approved charter that will be written and reviewed at the organizational meeting of the DMC. At this time, each data element that the DMC needs to assess will be clearly defined. The DMC will provide its input to Rafael Pharmaceuticals.

